#### Immune-Related Response Criteria Definitions

Target Lesion Definition	Non-Target Lesion Definition	New Measurable Lesions	New Unmeasurable Lesions	Percent change in tumor burden (including measurable new lesions when present)	Overall irRC Response
Complete Response	Complete Response	No	No	-100%	irCR
Partial Response	Any	Any	Any	≥ -50%	irPR
				<-50% to <+25%	irSD
				>+25%	irPD
Stable Disease	Any	Any	Any	<-50% to <+25%	irSD
				>+25%	irPD
Progressive Disease	Any	Any	Any	≥+25%	irPD

#### 11.3.1.5 Immune-Related Best Overall Response Using irRC (irBOR)

irBOR is the best confirmed overall response over the study as a whole, recorded between the date of first dose until the last tumor assessment before subsequent therapy (except for local palliative radiotherapy for painful bone lesions) for the individual subject in the study. For the assessment of irBOR, all available assessments per subject are considered.

irCR or irPR determinations included in the irBOR assessment must be confirmed by a second (confirmatory) evaluation meeting the criteria for response and performed no less than 4 weeks after the criteria for response are first met.

#### 11.3.1.6 Patient Reported Outcome Assessments

The PRO outcome measure for this study is as follows: Scores from the FACT-B assessment (Appendix C) and Rotterdam Symptom Checklist (Appendix D).

## **12. DATA REPORTING / REGULATORY REQUIREMENTS**

Adverse event lists, guidelines, and instructions for AE reporting can be found in Section 7.0 (Adverse Events: List and Reporting Requirements).

### **12.1 Data Reporting**

#### 12.1.1 Method

The Office of Data Quality (ODQ) will collect, manage, and perform quality checks on the data for this study.

#### 12.1.2 Responsibility for Data Submission

Investigative sites within DF/HCC or DF/PCC are responsible for submitting data and/or data forms to the Office of Data Quality in accordance with DF/HCC SOPs.

### **12.2 Data Safety Monitoring**

The DF/HCC Data and Safety Monitoring Committee (DSMC) will review and monitor toxicity and accrual data from this study. The committee is composed of clinical specialists with experience in oncology and who have no direct relationship with the study. Information that raises any questions about participant safety will be addressed with the Overall PI and study team.

The DSMC will review each protocol up to four times a year or more often if required to review toxicity and accrual data. Information to be provided to the committee may include: up-to-date participant accrual; current dose level information; DLT information; all grade 2 or higher unexpected adverse events that have been reported; summary of all deaths occurring within 30 days

of intervention for Phase I or II protocols; for gene therapy protocols, summary of all deaths while being treated and during active follow-up; any response information; audit results, and a summary provided by the study team. Other information (e.g. scans, laboratory values) will be provided upon request.

### **12.3 Multicenter Guidelines**

This protocol will adhere to the policies and requirements of the DF/HCC Multi-Center Data and Safety Monitoring Plan. The specific responsibilities of the Overall PI, Coordinating Center, and Participating Institutions and the procedures for auditing are presented in Appendix E.

- The Overall PI/Coordinating Center is responsible for distributing all IND Action Letters or Safety Reports to all participating institutions for submission to their individual IRBs for action as required.
- Mechanisms will be in place to ensure quality assurance, protocol compliance, and adverse event reporting at each site.
- Except in very unusual circumstances, each participating institution will order the study agent(s) directly from supplier. A participating site may order the agent(s) only after the initial IRB approval for the site has been forwarded to the Coordinating Center.

### **12.4 Collaborative Research and Future Use of Data and Samples**

Tissue, blood, stool, bodily fluids, and other materials derived from these will be collected in this study to analyze genes, DNA, RNA, proteins and cells for the study's correlative endpoints and potential future research, utilizing new types of biomarker testing as it becomes available.

These samples and any data generated as a part of these clinical trials may be used for future research studies and may be provided to collaborating investigators both within and outside of the DF/HCC for either correlative endpoints or secondary use. Samples and data may be shared with outside non-profit academic investigators, as well as with for-profit pharmaceutical investigators or commercial entities, with whom we collaborate. When samples or data are sent to collaborators and when any research is performed on them, all information will be identified with a code, and will not contain any PHI, such as name, birthday, or MRNs.

In order to allow the greatest amount of research to be performed on the specimens and information generated as a part of this trial, researchers in this study may share results of genetic sequencing with other scientists. De-identified specimen or genetic data may be placed into one of more publicly-accessible scientific databases, such as the National Institutes of Health's Database for Genotypes and Phenotypes (dbGaP). The results from the correlative research on this study will be shared with these public databases. Through such databases, researchers from around the world will have access to de-identified samples or data for future research. More detailed information, beyond the public database, may only be accessed by scientists at other research centers who have received special permission to review de-identified data.

## 13. STATISTICAL CONSIDERATIONS

### 13.1 Study Design/Endpoints

This is an open-label, single-arm, multicenter, phase 2 study of nivolumab 3 mg/Kg intravenously (IV) on day 1 of each 14 days plus Ipilimumab 1 mg/Kg IV every 6 weeks in subjects with hypermutated metastatic HER2- breast cancer previously treated with 0 to 3 chemotherapy regimens in the metastatic setting. The target enrollment is 30 evaluable patients. Patients that do not start protocol therapy will be considered unevaluable and will be replaced, therefore total enrollment may exceed 30 patients.

#### Primary Endpoint

The primary endpoint is ORR of nivolumab in combination with ipilimumab, according to RECIST 1.1 (Section 11), in patients with hypermutated HER2- metastatic breast cancer previously treated with 0 to 3 lines of chemotherapy in the metastatic setting.

#### Secondary endpoints include:

Secondary endpoints include the ORR of the combination according to immune-related response criteria (irRC) [Wolchok *et al.*, 2009] (Section 11), the clinical benefit rate according to RECIST 1.1 and irRC, PFS according to RECIST 1.1 and irRC, the OS, the ORR, PFS and OS of the combination according to RECIST 1.1 in the population with centrally confirmed hypermutated tumors ( $\geq 9$  mutations/megabase); and whether the cut off of  $\geq 14$  mutations/megabase is associated with the efficacy of this investigational therapy, assessed by ORR, PFS and OS.

#### Blood and Tissue correlative science objectives include:

- To characterize a broad array of immune markers in metastatic hypermutated HER2-negative breast cancers. (characterization will be based on histology, protein expression, and mRNA expression).
- To explore how different immunosuppressive and/or immune-stimulating immune marker profiles at baseline correlate with disease response to therapy (PFS, objective response assessed by RECIST 1.1 and immune-related response criteria).
- To characterize changes in tumor-infiltrating lymphocytes, PD-L1 expression and immune gene signatures in the tissue microenvironment (TME) from baseline to after 4 weeks of the experimental combination.
- To explore whether induction of changes in the immunosuppressive and/or immune-stimulating immune marker profile in TME correlates with disease response to therapy (response assessed by RECIST 1.1 and immune-related response criteria).
- To characterize serial changes in immune marker profile in peripheral blood mononuclear cells (PBMCs) and in plasma over the course of the trial treatment.
- To explore whether induction of changes in the immunosuppressive and/or immune-stimulating immune marker profile in PBMCs correlates with disease response to therapy (response assessed by RECIST 1.1 and immune-related response criteria).
- To investigate whether there is an immune marker in circulating PBMCs that corresponds to

tumor infiltrating lymphocyte (TIL) percentage in baseline tumor.

- To collect blood to study cell-free DNA for comparison to tumor specimens before and after immunotherapy.
- To explore whether the cut off of  $\geq 14$  mutations/megabase is associated with the efficacy of this investigational therapy, assessed by ORR per RECIST 1.1.
- To explore whether the cut off of  $\geq 14$  mutations/megabase is associated with the efficacy of this investigational therapy, assessed by PFS per RECIST 1.1
- To explore whether the cut off of  $\geq 14$  mutations/megabase is associated with the efficacy of this investigational therapy, assessed by OS per RECIST 1.1

#### Stool and microbiome correlative science endpoints:

Overall, we plan to describe the landscape of gut microbiota in patients with BC who will receive the combination of ipilimumab plus nivolumab, and the changes in their gut microbiota after 4 weeks of the combination. Statistical analyses of intestinal microbiota samples will be performed using R Statistical Language (v3.1.1) and GraphPad Prism (version 6.0e) software packages. Unpaired Mann–Whitney rank sum test (two-tailed) will be used for comparisons of continuous variables between two groups. Bar plots will be used to represent the data's mean at the center values, with error bars to indicate standard deviation. In order to explore the association of response (objective response according RECIST 1.1 and PFS) to baseline microbiota diversity, and changes from baseline in microbiota, inference will be based on Wilcoxon rank sum tests and estimates of predictive value along the continuous scales will be visualized using receiver operating characteristic (ROC) curves and reported with c-index and confidence intervals derived from variance estimates of Somers rank correlation. Unadjusted P-values will be considered significant for the Mann–Whitney rank sum test.

We will quantify microbiome features from amplicon, metagenome, metatranscriptome using established pipelines to identify strain-level taxonomic, functional gene, transcriptional, and microbially-mediated metabolite profiles associated with BC patients with and without immunotherapy. We will use modified multivariate linear modeling to identify statistically significant features associated with outcomes. Statistical tests for association with these outcomes and covariates will be performed using the sparse generalized linear model MaAsLin, which provides random effects models for both log-Gaussian and zero-inflated negative binomial link functions. Computational workflows for these steps are implemented as AnADAMA2 (<http://huttenhower.sph.harvard.edu/anadama>) workflows, a reproducible data handling environment that captures all provenance during the analysis process.

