#### **1.4 Correlative Objectives**

- 1.4.1 To characterize a broad array of immune markers in metastatic hypermutated HER2-negative breast cancers. (characterization will be based on histology, protein expression, and mRNA expression).
- 1.4.2 To explore how different immunosuppressive and/or immune-stimulating immune marker profiles at baseline correlate with disease response to therapy (PFS, objective response assessed by RECIST 1.1 and immune-related response criteria).
- 1.4.3 To characterize changes in tumor-infiltrating lymphocytes, PD-L1 expression and immune gene signatures in the tissue microenvironment (TME) from baseline to after 4 weeks of the experimental combination.
- 1.4.4 To explore whether induction of changes in the immunosuppressive and/or immune-stimulating immune marker profile in TME correlates with disease response to therapy (response assessed by RECIST 1.1 and immune-related response criteria).
- 1.4.5 To characterize serial changes in immune marker profile in peripheral blood mononuclear cells (PBMCs) and in plasma over the course of the trial treatment.
- 1.4.6 To explore whether induction of changes in the immunosuppressive and/or immune-stimulating immune marker profile in PBMCs correlates with disease response to therapy (response assessed by RECIST 1.1 and immune-related response criteria).
- 1.4.7 To investigate whether there is an immune marker in circulating PBMCs that corresponds to tumor infiltrating lymphocyte (TIL) percentage in baseline tumor.
- 1.4.8 To collect blood to study cell-free DNA for comparison to tumor specimens before and after immunotherapy.
- 1.4.9 To characterize the structure and function of the gut microbiome in patients with breast cancer prior to starting this clinical trial.
- 1.4.10 To determine whether pre-treatment characteristics of the structure and function of the gut microbiome in patients with breast cancer is associated with disease response to therapy (response assessed by RECIST 1.1 and irRC, and PFS).
- 1.4.11 To characterize changes in the structure and function of the gut microbiome of patients with breast cancer after 4 weeks of therapy compared to baseline.
- 1.4.12 To determine whether changes in the overall diversity of the gut microbiome, estimated by the Shannon Index, of patients with breast cancer after after 4 weeks of therapy is associated with disease response (response assessed by RECIST 1.1, irRC and PFS).

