#### 9.4.3 Analysis of RNA extraction from stool samples

Under [name] supervision, 16S rRNA analysis will be performed at The V4–V5 region of the 16S rRNA gene will be amplified and sequenced on an Illumina MiSeq platform at the Broad Institute. For each stool sample, replicate PCR reactions will be performed using modified universal bacterial primers designed to amplify the V4-V5 16S rRNA region: 563F (59-nnnnnnnn-NNNNNNNNNNNN-AYTGGGYDTAAAGN G-39) and 926R (59-nnnnnnnn-NNNNNNNNNNNN-CCGTCAATTYHTTTR AGT-39).

Using the Illumina TruSeq Sample Preparation procedure, PCR products will be quantified and pooled at equimolar amounts before Illumina barcodes and adaptors will be ligated on. The completed library will be sequenced on an Illumina MiSeq platform according to the Illumina recommended protocol. Sequences will be analysed using mothur version 1.31.115. Sequences were aligned using the Silva reference alignment as a template and potentially chimeric sequences were eliminated using the UChime algorithm^16. Five thousand sequences per patient were selected (mean 4,974, s.d. 150) and sequences with a distance-based similarity of  $\geq 97\%$  were grouped into OTUs using the furthest-neighbour algorithm. OTUs were classified using the Greengenes 16S rRNA reference database. OTU-based microbial diversity was estimated by calculating two diversity indices, Shannon and Inverse Simpson. OTU-based richness was determined by calculating the Chao richness estimate and constructing rarefaction curves. OTUs were grouped at different levels of classification (phylum, class, order, family and genus); at each level, OTUs that did not have a classification were grouped together by the highest available resolution. Feature selection of the intestinal microbiota's composition was performed on OTUs with an average abundance  $\geq 40.01\%$  in either patient group and grouped by phylotype.

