### **13.4 Analysis of Secondary Endpoints**

#### Efficacy Endpoints

All patients who initiated protocol therapy will also be evaluated for ORR according to irRC, and for CBR and PFS, according to RECIST. Clinical benefit is defined as CR, PR or SD  $\geq$  24 weeks according to RECIST 1.1. ORR according to irRC will be reported with 90% exact confidence intervals. CBR will be reported respectively with 95% exact confidence intervals. PFS will be analyzed using Kaplan–Meier product-limit estimates and will be plotted using Kaplan-Meier plots. PFS is defined as the time from study randomization to disease progression according to RECIST 1.1, medical judgment or death due to any cause, whichever occurred first. Patients alive without disease progression are censored at the date of last disease evaluation. The hazard ratio for each time-to-event endpoint will be estimated with 95% confidence intervals derived from the Cox proportional hazard model, but no hypothesis testing will be conducted.

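### Microbiota diversity against PFS: a two-group rank-sum test is planned for a censored endpoint, with no PFS groups and no rule for censored patients

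*Combined protocol and SAP*

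**What the plan says.** Section 1.4 makes PFS one of the outcomes for the microbiome work. Objective 1.4.10 concerns pre-treatment features, and objective 1.4.12 concerns "changes in the overall diversity of the gut microbiome, estimated by the Shannon Index". Section 9.4.3 treats diversity as a numerical index: "OTU-based microbial diversity was estimated by calculating two diversity indices, Shannon and Inverse Simpson".

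Section 13.1 (stool and microbiome endpoints) sets out one analysis for the "association of response (objective response according RECIST 1.1 and PFS) to baseline microbiota diversity", and likewise for change from baseline: "inference will be based on Wilcoxon rank sum tests and estimates of predictive value". The predictive-value part consists of ROC curves and a c-index, with a confidence interval from the variance of Somers rank correlation. The same paragraph says the rank-sum test "will be used for comparisons of continuous variables between two groups".

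Section 13.4 treats PFS as a time to event with Kaplan-Meier estimates: "Patients alive without disease progression are censored at the date of last disease evaluation". It adds: "The hazard ratio for each time-to-event endpoint will be estimated with 95% confidence intervals derived from the Cox proportional hazard model". It rules out significance tests on these estimates. Neither section refers to the other on this point.

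**The concern.** A rank-sum test needs every patient to carry a group label, and it has no way to use a censored time. Responder against non-responder provides that label. PFS provides one only after someone picks a time point and decides what to do with patients censored before it. The plan does neither.

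Two things follow. Turning PFS into two groups throws away follow-up time in a trial of about 30 patients. And because the cut and the censoring rule are open, they can be settled after the results are visible. The primary endpoint and all safety analyses are untouched.

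**Working it through.** **1. The plan's own figure.** There is none to reproduce: the documents state no power, effect size or numerical significance level for this analysis.

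**2. What each method needs.** Let x be diversity and τ a PFS cut.

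- Rank-sum: the label is 1 if progression-free at τ and 0 if progressed or dead before τ. It is unknown if censored before τ. The documents give neither τ nor the label for the third case.
- Cox: h(t | x) = h₀(t)·exp(βx). The score is the sum, over events, of (x of the patient with the event minus the mean of x among those still at risk). A censored patient stays in the risk sets until the last disease evaluation, which is the Section 13.4 rule. No cut is needed.

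**3. Illustrative power.** All inputs are assumptions except where marked:

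- 25 patients with usable samples (target enrolment 30, Section 13.1; missing stool is not a violation, Section 10)
- standard normal diversity; exponential PFS, median 17 weeks
- progression seen only at scans in weeks 6, 12, 18, 24, then every 12; censoring at the last scan
- two-sided 0.05; τ = 24 weeks, borrowed from the clinical-benefit definition in Section 11.1.5

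| Hazard ratio per SD, no censoring | Cox | 24-week split | Gap |
|---|---|---|---|
| 0.5 | 0.81 | 0.59 | 0.22 |
| 0.6 | 0.60 | 0.37 | 0.23 |
| 0.7 | 0.36 | 0.21 | 0.15 |
| 0.8 | 0.16 | 0.11 | 0.05 |

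Repeat runs fell within 0.03 of these values. With 1% drop-out per week (25% censored, 16% before week 24) and a hazard ratio of 0.5, Cox gives 0.72. The split gives 0.47 if early-censored patients are excluded and 0.41 if they are counted as failures.

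**4. Models that do not favour Cox** (no censoring):

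- threshold effect, hazard ratio 0.25 between diversity halves: 0.62 − 0.54 = 0.08
- effect starting only after week 6, hazard ratio 0.5 per SD: 0.55 − 0.39 = 0.16
- a mixture with 35% durable responders, odds ratio 4 per SD: 0.40 − 0.35 = 0.05

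**5. How far the undefined rule alone moves the result.** A second set of assumptions: 30 patients, median PFS 4 months, log-time slope 0.6 per SD (hazard ratio exp(−0.6) ≈ 0.55), a cut at 5.5 months, uniform censoring from 0.5 to 8 months (heavier) or to 16 months (lighter). Power by grouping rule:

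| Rule | Heavier censoring | Lighter censoring |
|---|---|---|
| Exclude early-censored | 0.25 | 0.44 |
| Count them as progressed | 0.14 | 0.32 |
| Count them as progression-free | 0.44 | 0.48 |
| Event v censored | 0.42 | 0.39 |
| Median split of observed times | 0.22 | 0.31 |
| Cox, continuous diversity | 0.56 | 0.68 |

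**6. False positives.** With no true association and equal follow-up, rejection is 0.04 to 0.06 for every version in both sets of assumptions. If weekly drop-out is 3% in the low-diversity half and 0.5% in the high half, it is 0.05 (split, excluded), 0.11 (split, counted as failures), 0.28 (rank-sum on observed times) and 0.06 (Cox).

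**The case against.** **The c-index already covers PFS.** Section 13.1 applies it to PFS as well as to objective response, and a c-index built on Somers rank correlation can be computed for censored data. This stands in part: it would be wrong to say that nothing in the section could handle PFS. But the censored version is not named, the measure is paired with ROC curves, and the inference is placed on the rank-sum test.

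**Cox is already planned.** Section 13.4 promises a hazard ratio for every time-to-event endpoint. In a single-arm trial that needs a covariate, so diversity might be meant. The support is weak. No covariate is named, and the surrounding text looks carried over from a randomised trial: PFS runs from randomization, and toxicity is compared between two arms.

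**Twenty-four weeks is the obvious cut.** A reader might infer that the split is implied. The documents use 24 weeks for clinical benefit only and never as a PFS grouping. It serves here as an assumption.

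**The gain rests on a large assumed effect.** This stands. At a hazard ratio of 0.8 neither method is informative, and when the model does not favour Cox the gap is modest.

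**The work is exploratory.** True: Section 10 says so of the stool collections, and no decision about the regimen depends on them.

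**Conclusion.** The point holds as a low-priority improvement. The stated test suits objective response and does not suit PFS, and the plan leaves open the PFS groups, the handling of censored patients, the type of c-index and any link to the Cox sentence.

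The cost is power and pre-specification. In the illustration it is about 22 points at a hazard ratio of 0.5 per SD, 15 at 0.7, 5 at 0.8, and 5 to 16 under the alternative models. Effect size, median PFS, drop-out and the 24-week cut are all assumed.

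A reader might go further and infer that the planned p-values are invalid. The documents do not support that. With equal follow-up, any single rule fixed in advance keeps its error rate. Inflation needs follow-up that differs with diversity, together with a rule that counts early-censored patients as failures or ranks observed times. Section 5.6 keeps following patients who leave therapy without progression until first progression, which limits this, although scans may stop when another anti-cancer therapy starts. Nor does anything here bear on the ORR conclusion.

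**What to change.** In Section 13.1, limit the rank-sum test and ROC curve to objective response, and add for PFS:

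> Diversity will be related to PFS by a Cox model with diversity as a continuous covariate and censoring as in Section 13.4. The hazard ratio per SD with 95% CI and the censored-data c-index will be reported, without a formal test. For change in diversity, PFS will be counted from the on-treatment stool sample, among patients alive and progression-free at that time.

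If the team wants a p-value, it should be labelled exploratory and reconciled with Section 13.4, which rules out hypothesis testing. If a fixed-time PFS split is kept as well, state the time and the rule for patients censored before it.

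The cost is a few sentences and a few lines of code. No new data are needed, and the model is one that the plan already names. There are two downsides. The Cox model assumes proportional hazards and a log-linear effect, and it gains less when these fail. Starting the clock at the second sample drops the few patients who progress before it.

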- 1.4.13 To determine if the abundance and functional profile of specific gut bacteria are associated with objective response therapy (response assessed by RECIST 1.1, irRC and PFS).
- 1.4.14 To evaluate the functional pathways that may play a role as a predictive biomarker of disease response to therapy (response assessed by RECIST 1.1, irRC and PFS).
- 1.4.15 To determine whether pre-treatment characteristics of the structure and function of the gut microbiome in patients with breast cancer is associated with therapy-induced grade  $\geq 2$  diarrhea.
- 1.4.16 To explore whether the cut off of  $\geq 14$  mutations/megabase is associated with the efficacy of this investigational therapy, assessed by ORR per RECIST 1.1.
- 1.4.17 To explore whether the cut off of  $\geq 14$  mutations/megabase is associated with the efficacy of this investigational therapy, assessed by PFS per RECIST 1.1
- 1.4.18 To explore whether the cut off of  $\geq 14$  mutations/megabase is associated with the efficacy of this investigational therapy, assessed by OS per RECIST 1.1

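### Microbiome rank tests are to be called significant on unadjusted p-values, and no error control is stated for them or for the MaAsLin feature search

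*Combined protocol and SAP*

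**What the plan says.** Section 13.1, under the stool and microbiome heading, sets the rule for the Mann–Whitney test: "Unadjusted P-values will be considered significant". It assigns that test broadly: "Unpaired Mann–Whitney rank sum test (two-tailed) will be used for comparisons of continuous variables between two groups". For the association of RECIST 1.1 response and PFS it ties the test "to baseline microbiota diversity, and changes from baseline in microbiota, inference will be based on Wilcoxon rank sum tests". ROC curves and a c-index with confidence intervals accompany the tests.

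The next paragraph gives the wide search a different method. Established pipelines are used "to identify strain-level taxonomic, functional gene, transcriptional, and microbially-mediated metabolite profiles", and testing for association with outcomes "will be performed using the sparse generalized linear model MaAsLin". The aim is to find features that reach statistical significance, but no significance level, false discovery rate or other control is given.

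Among the objectives, 1.4.13 is "To determine if the abundance and functional profile of specific gut bacteria are associated with objective response therapy", and 1.4.14 looks for pathways that predict response. Section 9.4.3 groups OTUs at five taxonomic ranks, names three diversity or richness measures (Shannon, Inverse Simpson and Chao), and applies an abundance filter to OTUs. The number of features kept is not stated anywhere.

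**The concern.** A plan that says nothing about multiplicity leaves room for a sensible choice at analysis. Here, for the rank tests, the plan makes the choice, and it is to ignore multiplicity. An analyst who compares each taxon between responders and non-responders by Mann–Whitney, and reports every small p-value as significant, is following the text. If MaAsLin is used for the screen instead, nothing in the plan limits the error rate there either.

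Section 2.7.2 gives the intended use. Markers of response could spare resistant patients the risks of treatment, and species linked to response could guide changes to the gut flora. A list of taxa labelled significant could steer that work even if it arose by chance.

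**Working it through.** The documents state no error rate, power or number of tests for the microbiome work, so there is no figure of theirs to reproduce.

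**Inputs**
- Multiplicity rule: none for rank tests; not stated for MaAsLin (section 13.1).
- Sidedness: two-sided (section 13.1).
- Significance level: not stated; 0.05 per test is assumed.
- Number of tests m: not stated; a range is shown.
- Patients: 30 (section 13.1), assuming that all give stool. Responders: 25% × 30 = 7.5, taken as 8, using the target rate in section 13.2.

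**Formulas, no feature truly associated**
- Expected false positives = 0.05 × m. This does not depend on correlation between features.
- Chance of at least one, independent tests = 1 − 0.95^m.

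The last three columns simulate Mann–Whitney tests with 8 responders and 22 non-responders, 1,000 replicates, no ties, and a common latent correlation ρ between features.

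| m | Expected | 1 − 0.95^m | Simulated, ρ = 0 | ρ = 0.3 | ρ = 0.6 |
|---|---|---|---|---|---|
| 3 | 0.15 | 0.14 | – | – | – |
| 5 | 0.25 | 0.23 | – | – | – |
| 10 | 0.5 | 0.40 | – | – | – |
| 20 | 1 | 0.64 | 0.61 | 0.52 | 0.32 |
| 50 | 2.5 | 0.92 | 0.91 | 0.79 | 0.51 |
| 100 | 5 | 0.994 | 0.99 | 0.94 | 0.67 |
| 200 | 10 | >0.999 | 1.00 | 0.98 | 0.79 |

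**What moves these figures**
- *Discreteness.* The exact test has true size 0.041 to 0.049 for 2 to 10 responders of 30. At m = 100 the independent figure becomes 0.985 to 0.993.
- *Correlation.* It lowers the chance of any false positive but hardly changes the count: the simulated mean at m = 100 is 4.4, 4.4 and 4.8 for ρ = 0, 0.3 and 0.6.
- *Sparse features.* With 70% tied zeros (500 replicates), the m = 100 chances are 0.98, 0.93 and 0.78.

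**A narrow reading.** Suppose the rank tests cover only the three measures in section 9.4.3, at baseline and as change, against the two outcomes in the rank-test text. Then m = 3 × 2 × 2 = 12, the expected count is 0.05 × 12 = 0.6, and 1 − 0.95^12 = 0.46. The three measures are correlated, so 0.46 is an overstatement. The count of 12 is illustrative, since the plan does not enumerate the tests.

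**After correction.** Across all simulated settings, the chance of any false positive was 0.32 to 1.00 unadjusted and 0.006 to 0.054 with Benjamini–Hochberg at 0.05.

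**The case against.** A reader might infer that the unadjusted rule governs a screen of OTUs at five taxonomic ranks plus pathways, against four outcomes, so that false predictive bacteria are almost certain. The documents do not support that.

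- *Scope.* The rank-test text names diversity and change from baseline. The broad feature search goes to MaAsLin, where adjustment is unstated, not ruled out. Section 9.4.3 describes how OTUs are grouped and names no hypothesis test; parts of it are in the past tense and report achieved sequencing figures, so it is weak evidence of a test plan.
- *Outcomes.* The rank-test text names RECIST 1.1 response and PFS only. Response by irRC and grade 2 or higher diarrhea appear in the objectives, which do not assign them this test. Multiplying the expected count by four is not warranted.
- *Certainty.* It needs a significance level, a feature count and independence, none of which the documents give. Taxa nested from phylum to genus are not independent.
- *Consequence.* The study calendar calls the stool collections exploratory, section 13.1 aims to describe and explore, and effect estimates are reported beside the tests. Neither the two-stage rule nor the primary analysis uses these p-values.

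All four limits stand. They do not make the rule sound. The general assignment of the test reaches taxon abundance, and change from baseline is not confined to diversity. Exploratory status is a reason not to attach the word significant to unadjusted results, and intervals for the c-index do not correct for selecting among many features.

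**Conclusion.** The point holds within those limits. The plan declares unadjusted rank-test p-values significant, and it states no significance level, number of tests or error control for these tests or for MaAsLin. At an assumed 0.05, each null feature tested adds 0.05 expected false positives whatever the correlation. The chance of at least one runs from about 14% to 40% for 3 to 10 independent summary tests to 92% to 99% for 50 to 100 independent features, and falls to about 67% at 100 features with latent correlation 0.6. Which part of that range applies cannot be settled from the documents. False positives should be expected if dozens of features are tested; near certainty cannot be claimed. The consequence is confined to the microbiome objectives, chiefly 1.4.13 and 1.4.14. It does not make those objectives unanswerable, because effect estimates remain, and the conclusion on ORR is untouched.

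**What to change.** Delete the sentence on unadjusted p-values and replace it with wording such as:

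*Feature-level tests (taxa, genes, transcripts, metabolites, pathways), whether by rank sum test or MaAsLin, will be adjusted by the Benjamini–Hochberg method within each feature family and outcome, at a false discovery rate fixed before analysis. Unadjusted p-values will be shown beside adjusted ones. The lead diversity test is baseline Shannon index against RECIST 1.1 response, at a stated two-sided alpha. Other diversity indices, time points and outcomes will be descriptive or adjusted. All microbiome results are hypothesis-generating.*

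Also state the abundance filter, report the number of features tested, and say which variables and outcomes the rank test covers, including how PFS enters a two-group comparison. Naming Shannon alone would not be enough: objectives 1.4.10 and 1.4.12 cover both baseline and 4-week change against several outcomes, so the lead time point and outcome must be fixed too. Baseline Shannon against RECIST response is one reasonable choice.

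The cost is SAP wording and trivial computation, with no extra patients, samples or visits. The downside is fewer nominally significant taxa, and with very few responders perhaps none. The smallest possible exact two-sided p-value is 2/C(30, r): 2/435 = 0.0046 for 2 responders, 2/4,060 = 0.00049 for 3 and 2/27,405 = 0.000073 for 4. Against a Bonferroni threshold of 0.05/m these allow at most 10, 101 and 685 features. Benjamini–Hochberg is less strict when several features are small together, but the limit is a reason to filter features before testing.
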